1.1. Background

Obesity is a risk factor for the development of asthma (approximately 250,000 cases per year of asthma in the U.S. are related to obesity).¹ These patients have poorly controlled asthma (with a nearly 5-fold risk of hospitalization) and do not respond as well to conventional controller therapy as lean asthmatics.²⁻⁶ Obesity particularly affects minority populations;⁷ non-Hispanic blacks have the highest age-adjusted rates of obesity (47.8%) followed by Hispanics (42.5%), non-Hispanic whites (32.6%), and non-Hispanic Asians (10.8%). This is thought to account in part for the disparities of asthma in minority populations; there is a pressing public health need to develop interventions specifically for obese asthmatics.

One medication that might be particularly useful for the treatment of asthma in obesity is roflumilast, a medication currently used in the treatment of chronic obstructive pulmonary disease. Data in clinical trials support efficacy of this medication in the treatment of asthma,⁸ though it has never been approved for treating asthma in the general population, likely because of concern about side-effects; but these “side-effects” may actually contribute to efficacy in the treatment of asthma in obesity.

Roflumilast has efficacy in mouse-models of asthma and obesity: roflumilast reduced airway remodeling and reactivity in a non-allergic mouse model of obese asthma, and also airway reactivity, inflammation and remodeling in an allergic mouse model of obese asthma.⁹ These effects are likely related both to direct effects on inflammatory cells and cells resident in the airway, and also to the beneficial metabolic effects of roflumilast. Roflumilast has significant beneficial incretin-like metabolic effects in patients with the metabolic syndrome,¹⁰ and so might be helpful to mitigate the metabolic dysfunction associated with asthma in obese patients.¹¹ In addition, roflumilast promotes weight loss, especially in the obese,¹²⁻¹⁵ and significant weight loss may improve asthma control in obesity. These direct effects of roflumilast in the airway, and “side-effects” on metabolism and weight loss, make this medication a particularly exciting candidate to treat asthma in obese patients.

1.2. Primary objective

The primary objective of this proposal is to perform a pilot placebo controlled trial of roflumilast for the treatment of poorly controlled obese asthmatics in select centers of the American Lung Association-Airways Clinical Research Centers (ALA-ACRC) to determine the effectiveness and tolerability of our intervention in obese asthma.

[figure not shown]
The current proposal comprises a pilot randomized, placebo-controlled trial of roflumilast in obese patients with poorly controlled asthma in five centers of the American Lung Association-Airways Clinical Research Centers (ALA-ACRC).

The results of this trial will lay the groundwork for a definitive multicenter clinical trial of roflumilast for the treatment of poorly controlled asthma in obese patients. If ultimately successful roflumilast would represent a new treatment for obese patients with asthma, a patient population refractory to current therapies that represents the majority of poorly controlled asthmatics in the United States.

1.3. Study design

A 24 week, randomized, double-masked, placebo controlled trial in 38 participants.

1 week baseline ← 24 week treatment →

V1	V2	V3	V4	V5	V6	V7
wk-1	wk0	wk2	wk6	wk12	wk18	wk24

2. Methods

2.1. Eligibility criteria

2.1.1. Inclusion criteria

- Physician diagnosis of asthma and on regular prescribed controller therapy for at least 3 months
- Previous (within five years) evidence of at least a 12% increase in FEV₁ after inhaling 2-4 puffs of albuterol or a positive methacholine challenge or patient reported history of improvement of asthma exacerbation after a course of systemic or inhaled corticosteroids.
- Age: ≥18 years of age
- Obese: BMI > 30 kg/m²
- Poorly controlled asthma: Asthma Control Test Score < 20, or use of rescue inhaler, on an average of > 2 uses/week for preceding month, or nocturnal asthma awakening, on an average of 1 or more times / week in preceding month, or ED/hospital visit or prednisone course for asthma in past six months.
- Ability and willingness to provide informed consent

2.1.2. Exclusion criteria

- Participation in an investigational study within the past 4 weeks
- Physician diagnosis of chronic obstructive pulmonary disease
- Any condition that puts the participant at risk from weight loss as judged by the site physician
- Liver cirrhosis
- Major psychiatric disorders such as generalized anxiety disorder, major depressive disorder, history of suicidal ideation/ attempt, panic disorder, post-traumatic stress disorder, schizophrenia, schizoaffective, substance abuse or other disorders that in the opinion of the study physician that would affect study participation
- > 0 time use of illicit drugs in the past 12 months
- > 0 time use of cannabis in the past 12 months
- Uncontrolled depression as defined by a score of 15 or greater on the depression questions of the PHQ-9
- Suicidal ideation (a score of greater than 0 on Question 9 on the PHQ-9)
- Uncontrolled anxiety as defined by a score of 10 or greater on the anxiety questions of the GAD-7
- Pregnancy/lactation
- Females of childbearing age who do not agree to practice an adequate birth control method (abstinence, combination barrier and spermicide, or hormonal) for the duration of the study.
- Greater than 20 pack year smoking history, or smoking within the last 6 months.
- History of bariatric surgery
- Drugs metabolized by cytochrome P450 (rifampicin, phenobarbital, carbamazepine, phenytoin, erythromycin, ketoconazole, cimetidine, fluvoxamine, enoxacin, oral contraceptives containing ethinyl estradiol with gestodene).
- Currently on roflumilast or theophylline (patient may wash out of these medications for 4 weeks prior to visit 1).
- Intention to move out of area within the next 6 months

2.2. Rationale for study duration

We base the duration of the study on the likely time needed to induce weight loss, as well as to improve metabolic control.^{8,10,16} We anticipate that this will be the duration of the definitive clinical trial, and so it will be important to ascertain the feasibility of a trial of this duration in our patient population of interest.

2.3. Rationale for dose of active drug

We base the dose of active drug on the dose that is FDA approved for use in COPD in this country, and has also shown efficacy in the treatment of asthma⁸ and metabolic disorders:¹⁰ this will be 500 µg, once per day. For the first two weeks we will treat with 500 µg every other day to increase tolerability of the medication.

2.4. Rationale for the seven centers

Collaborating sites: Northwestern University Feinberg School of Medicine, Mount Sinai Icahn School of Medicine, Duke University, University of Arizona, University of Alabama Lung Health Center, University of Illinois – Chicago, and the University of Vermont. Johns Hopkins University will be the Data Coordinating Center (DCC) for the trial.

We will perform this study in seven centers that have a strong record of recruitment and working together as part of the ALA-ACRC, and that represent diverse populations within the network. We will need to recruit 5-6 patients per site within an approximate 12 month period to complete all procedures and study analysis within the time-frame of this proposal, and this is a reasonable recruitment target for these centers. These centers represent diverse patient population, and so if successful, this will likely predict success in the multi-center trial. Many of these centers have established research programs on obesity in asthma.

2.5. Background asthma care

Participants will be treated in accordance with asthma guidelines and best practices using materials that have been already developed by the ALA-ACRC. This includes a written asthma action plan based on peak flow, and instruction on inhaler technique and avoidance of asthma triggers. All participants will be prescribed controller medication that includes medium dose inhaled corticosteroids and additional add-on treatments as needed. Participants who have a regular asthma care provider will continue to receive care from that source. If not, they will be referred to an asthma care provider associated with the study site. All participants will be provided with an asthma action plan, but we will not provide routine asthma care.

2.6. Randomization and drug distribution

Participants will be randomly assigned with an equal allocation to receive either active treatment or matching placebo for 6 months. The treatment assignment will be double-masked, neither the participant nor the clinical center investigators will be informed of the treatment group. Randomization will be accomplished with an auditable, documented generation scheme that produces a reproducible order of assignment, this schema will be generated by the DCC. Randomization will be stratified by center and age and each clinical center randomization schedule will be based on randomly permuted blocks of varying size to ensure appropriate balance between the treatment groups within a center.

Drug bottles will be shipped to the centers from Temple University. These bottles will be identified by a number to maintain masking of the study site. Upon randomization, the site will be advised of the bottle number to issue a particular participant.

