2.8. Randomization and blinding

Treatment assignments will be stratified by clinic and the allocation ratio will be (1:1). Randomization will be accomplished by keying eligibility data into the data system; after verification of eligibility, a treatment assignment number corresponding to unique study kit will be assigned. Study kits will be labeled with two-part tear-off labels with unique identifiers. The tear-off label is affixed to a study form when the kit is assigned to a participant and the information is keyed into data system to verify that assigned treatment was given to the participant.

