3.1. Primary analysis

The primary statistical analysis will be an unadjusted comparison of 24-wk change in ACT between treatment groups. A linear mixed effects model will be used to model the change in ACT over time. A saturated means model, including indicators for each time point, treatment and treatment by time interaction, will be specified and a random effect for individual will be used to account for the repeated measurements over time. The 24-week treatment by time interaction term represents the difference in change in ACT between the treatment groups, i.e. the primary outcome. If the data are non-normal, then transformations and non-parametric alternatives (e.g. Wilcoxon Rank-Sum test comparing the raw differences from baseline to 24-weeks between treatment groups) will be explored. If imbalances in influential baseline variables are present, then secondary analyses using appropriate stratification or adjustments will be done. Sensitivity analyses using alternate mean and covariance structures will also be performed. Analyses will be done based upon principles of intention to treat, i.e. all data from all randomized participants will be included in the analysis.

Secondary analyses will focus on the effects of additional covariates including age, gender, site, BMI >40, baseline ACT score, and adherence with treatment. These models will build on primary analysis described above. Potentials risk factors will be added as a main effect to reduce variability and interaction effect to identify potential subgroup effects. Analyses using adherence measures will be performed to explore dose-response relationships.

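### Sections 2.6 and 2.8 disagree on whether age is a randomization stratum, give no age bands, and the unadjusted primary model in 3.1 carries no stratum: a minor point to reconcile before unmasking

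*Combined protocol and SAP*

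**What the plan says.** On allocation, section 2.6 states: "Randomization will be stratified by center and age and each clinical center randomization schedule will be based on randomly permuted blocks of varying size". Section 2.8 states: "Treatment assignments will be stratified by clinic and the allocation ratio will be (1:1", without mention of age. The only age figure in the protocol is the eligibility limit of 18 years, so no stratification cut-point can be found. Section 2.6 gives the coordinating center the task of generating a documented schedule, which may hold one.

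On analysis, section 3.1 states: "The primary statistical analysis will be an unadjusted comparison of 24-wk change in ACT between treatment groups". The model has visit, treatment, their interaction and a random effect for the individual. Age and site come in later: "Secondary analyses will focus on the effects of additional covariates including age, gender, site, BMI >40, baseline ACT score, and adherence with treatment". These enter as follows: "Potentials risk factors will be added as a main effect to reduce variability and interaction effect to identify potential subgroup effects". Section 3.1 also foresees two further variations: "If imbalances in influential baseline variables are present, then secondary analyses using appropriate stratification or adjustments will be done" and "Sensitivity analyses using alternate mean and covariance structures will also be performed". If the data are non-normal, one alternative is a "Wilcoxon Rank-Sum test comparing the raw differences from baseline to 24-weeks between treatment groups".

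**The concern.** If center and clinic are the same unit, the conflict is whether age was a stratum. The two sections cannot both be complete, and the section 2.6 scheme cannot be reproduced from the protocol without age bands. The trial report will have to state one scheme.

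The second issue is that the analysis does not follow the design. Stratified allocation removes stratum differences from the treatment estimate. A comparison of 24-week changes that ignores the strata still counts those differences as error, so its interval is too wide if the strata predict change. None of the variations in section 3.1 is specified to carry the randomization strata. Adding age or site as a main effect does not do so either: with complete data it leaves the 24-week treatment-by-visit estimate unchanged.

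At stake is some precision in the one-sided 90% limit that informs whether to run the definitive trial.

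**Working it through.** **Inputs from the protocol.** 38 participants (section 3.3), seven centers with 5 to 6 patients each (2.4), 1:1 allocation (2.6, 2.8), SD of ACT change 5, definitive-trial difference 2.8, pilot sized on 28 to 34 (3.3).

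**Assumptions.** The documents do not give these: two age bands split 50:50, block sizes 2/4 or 4/6, and a share R2 of the variance of change explained by the strata, divided equally between age and clinic. R2 is taken as 0, 0.10 and 0.20.

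**1. The plan's own figures.** The one-sided 90% limit at zero effect, in SD units, is 1.2816 × √(4/N). N = 28 gives 0.4844 and N = 34 gives 0.4396, against 0.4844 and 0.4397 in the table. Per site, 38/7 = 5.4. These reproduce.

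**2. The two schemes.** Clinic only: 7 strata of 5.4. Center by two age bands: 14 strata of 38/14 = 2.7. In 20,000 simulated allocations, a split of 22:16 or worse occurred in 2 to 4% (clinic only) and 11 to 21% (center by age, 50:50 or 70:30 split). At 22:16 the SE is only 1.3% wider.

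**3. Error rate at nominal 5%.** If strata were perfectly balanced, the unadjusted two-sided rate would be 2 × [1 − Φ(1.96/√(1 − R2))], which is 3.9% at R2 = 0.10 and 2.8% at 0.20. Incomplete blocks weaken this. Simulation with all 38 complete (20,000 null trials per setting; Wilcoxon 6,000):

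| Analysis, center-by-age strata | R2 = 0 | 0.10 | 0.20 |
|---|---|---|---|
| Unadjusted change score | 4.9–5.1% | 4.4% | 3.7% |
| Wilcoxon on raw differences | 4.7–4.9% | 3.6–4.1% | 3.9–4.0% |
| Planned random-intercept model | 4.8–5.0% | 5.0% | 5.1–5.2% |

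With clinic-only strata, the planned model gave 5.0 to 5.9% and the unadjusted change score 4.1 to 5.2%.

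**4. Mean one-sided 90% limit at zero pilot effect (ACT points, change-score model, center-by-age).** With 38 complete, unadjusted is t(0.9, 36) × 1.615 = 2.11. With fixed clinic plus age terms it is t(0.9, 29) × SE: 2.18–2.22 at R2 = 0 (SE 1.661–1.694), 2.07–2.11 at 0.10 (1.578–1.608) and 1.95–1.99 at 0.20 (1.487–1.515). With random loss down to the numbers that the pilot was sized on:

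| Completers | R2 | Unadjusted | Clinic plus age |
|---|---|---|---|
| 34 | 0 | 2.23–2.24 | 2.33–2.40 |
| 34 | 0.10 | 2.25 | 2.23–2.27 |
| 34 | 0.20 | 2.24–2.25 | 2.10–2.14 |
| 28 | 0 | 2.49 | 2.69–2.76 |
| 28 | 0.10 | 2.48–2.50 | 2.55–2.61 |
| 28 | 0.20 | 2.49–2.50 | 2.41–2.46 |

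At R2 = 0 the widening runs from 2.33/2.24 = 1.04 to 2.76/2.49 = 1.11.

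**5. Age alone.** An age term widens the limit by about 1% if age is uninformative, and narrows it by 1 to 5% at R2 of 0.10 to 0.20 when half of that is due to age.

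**6. Main effects against terms that act on the change.** In 60 simulated trials with 15% dropout (assumed) and R2 = 0.10, age and clinic main effects moved the mixed-model 24-week estimate by 0.04 ACT points on average (maximum 0.13). Strata-by-visit terms moved it by 0.48 (maximum 1.69). This shows which terms act on the estimate, not that the estimate improves.

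**The case against.** The case for leaving the primary analysis alone is strong. Unadjusted is an explicit choice. Age and site are already named as secondary covariates, and adjustment for imbalance and alternate mean structures are foreseen. Section 2.8 does not say clinic alone; it may simply be less complete than 2.6. Nothing in the documents shows that center or age predicts ACT change. The simulations also assume no other variation between patients in change.

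Much of this stands. A reader might infer that the omission biases the result, or that the planned test has the wrong error rate. The first is not so. For the second, the planned model held 4.8 to 5.2% under center-by-age strata. The conservatism belongs to a change-score test that the plan does not name and to a fallback that is only conditional. Under clinic-only strata the planned model leaned, if anything, slightly the other way.

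A reader might also infer that clinic must go into the primary model. That is not supported. With six visits, clinic main effects and clinic-by-visit terms add 6 + 30 parameters, and age adds 1 + 5: 42 extra terms for 38 patients, in a model whose error rate was not tested. The tested change-score version loses precision at 28 to 34 completers unless R2 is near 0.20, and drops patients without a 24-week ACT, against the intention-to-treat statement in 3.1.

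What the objection does not remove is the disagreement between 2.6 and 2.8, or the absence of any analysis specified to carry the strata.

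**Conclusion.** The point holds as a minor one. The two descriptions of the randomization must be reconciled, and the age bands stated if age was used. The analytic consequence is small: no bias, no demonstrated fault in the planned random-intercept model under center-by-age strata, and mild conservatism for a change-score or Wilcoxon comparison. A reader might expect the go/no-go reading to change. It does not: every mean limit at zero pilot effect, adjusted or not, is at most 2.76 and so below 2.8.

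The text comparison is certain. The sizes rest on the assumed R2, age bands, age split and block sizes. The gain from age adjustment was calculated for a change-score model; within the random-intercept model no clear gain from adjustment was seen.

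**What to change.** 1. Have the coordinating center confirm the scheme actually generated. Keep it and all existing assignments. State that one scheme, with age bands if used, in both 2.6 and 2.8.
2. Before unmasking, if age was a stratum, add it to the primary analysis so that it acts on the 24-week change: age-by-visit terms in the mixed model, or age in a change-score model. The first keeps the mixed model with every randomized participant, as 3.1 intends.
3. Prespecify a clinic-adjusted analysis of 24-week change (plus age, if used) as a named sensitivity analysis, not as the primary. If clinic is random, name a small-sample degrees-of-freedom method: with residual degrees of freedom, a random clinic effect rejected 5.3 to 5.9% under the null.
4. Report the unadjusted result alongside.

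The cost is one check of the schedule, changes of wording, and submission to the DSMB if this counts as a significant amendment under section 5. The statistical cost of the age term is a limit about 1% wider if age is uninformative. The sample size does not change. Sparse center-by-age cells should be weighed when strata are chosen for the definitive trial, not by changing them in this one.

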2.7. Source of study medication

We will purchase drug, and arrange for matching active drug and placebo through Temple University Research Pharmacy. Drug will be distributed from Temple University to the individual sites. DCC will instruct Temple University on the set of bottle numbers to dispense.

2.8. Randomization and blinding

Treatment assignments will be stratified by clinic and the allocation ratio will be (1:1). Randomization will be accomplished by keying eligibility data into the data system; after verification of eligibility, a treatment assignment number corresponding to unique study kit will be assigned. Study kits will be labeled with two-part tear-off labels with unique identifiers. The tear-off label is affixed to a study form when the kit is assigned to a participant and the information is keyed into data system to verify that assigned treatment was given to the participant.

2.9. Procedures

Sites conducting remote follow up visits must use a secure (password protected) zoom link or other secure online communication method. Participants who are followed up remotely, will complete some questionnaires over the phone and mail back the rest of the questionnaires to the site.

Outline of Study Visits							
Week	-1	0	2	6	12	18	24
Visit number	V1	V2	V3	V4	V5	V6	V7
Consent	•						
Baseline/interim history	•	•	•	•	•	•	•
Randomization		•					
Pill distribution†		•		•	•		
Pill distribution‡		•			•		
Review of paper/electronic diary cards		•	•	•	•	•	•
Pill Counts			•	•	•	•	•
Asthma Control	•	•	•	•	•	•	•
Anxiety/depression questionnaires	•	•	•	•	•	•	•
GSRS	•	•	•	•	•	•	•
QOL	•	•	•	•	•	•	•
Anthropometrics	•	•	•	•	•	•	•
Fasting Blood draw¥		•					•
Pregnancy test*	•	•	•	•	•	•	•
End of study questionnaire							•

† if dose frequency is every day since V3

‡ if dose frequency is every other day since V3

¥ conduct blood draw only if site permits it

*for women of child-bearing potential and participating in remote follow up participants will be mailed testing kit, and asked to send photo of result to coordinator

- Participants will be trained on how to perform peak expiratory flow at the study visit and sent home with asthma action plan.
- Asthma paper/electronic diary cards will be completed by participants throughout the study to record daily morning peak expiratory flow (PEF), daily asthma symptom scores, beta-agonist use, nocturnal asthma awakenings, and health care use.^{17,18} Diary data are used to identify episodes of poor asthma control and days with no asthma symptoms (asthma-free days).
- The Asthma Control Test (ACT) is a 4-week recall questionnaire that measures asthma control.¹⁹
- The Marks Asthma Quality of Life Questionnaire (Marks AQLQ) assesses asthma specific quality of life.²⁰
- The Asthma Symptom Utility Index (ASUI) is a 2-week utility-weighted asthma symptom questionnaire.²¹
- GI side effects will be assessed with the Gastrointestinal Symptom Rating Scale. This is a 15-item instrument with five subscales (reflux, diarrhea, constipation, abdominal pain and indigestion) that was originally developed to assess the symptoms associated with the most common GI disorders, and has previously been used to assess tolerability of medications. The five subscales of the questionnaire produce a mean score ranging from 1 (no discomfort) to 7 (very severe discomfort).²²
- Medical Outcomes Study (SF36) is a measure of general health related quality of life which correlates with asthma outcomes.^{23,24}

- The Patient Health Questionnaire for Depression and Anxiety (PHQ9 and GAD7) will be used. The Patient Health Questionnaire is a diagnostic tool for mental health disorders used by health care professionals that is quick and easy for patients to complete. We have used this questionnaire in prior ALA-ACRC studies, and so the centers are familiar with its use. We will use sections specific to mood (PHQ-9) and anxiety (GAD-7). The PHQ-9, a tool specific to depression, scores each of the 9 DSM-IV criteria based on the mood module from the original PRIME-MD. The GAD-7 was subsequently developed as a brief scale for anxiety and scores seven common anxiety symptoms.^{25,26}
- Anthropometrics will include blood pressure, height and weight, and waist and hip circumference per NHANES III.²⁷ Digital scales will be given to participants at visit 2 to take home to measure weight. Participants will be asked to send a photo of the weight shown on the scale along with their feet to the coordinator.
- Adverse effects will be assessed by open-ended questions at each visit and rated in severity.
- Interval health history will be recorded at each clinic visit. Records of all hospitalizations and, if necessary, deaths are obtained for verification of diagnoses and assessment of safety issues.
- Baseline questionnaires and exam will be administered to ascertain demographics including self-reported ethnicity and race, general health, co-morbid conditions, asthma symptoms, and medication use.
- Assessment of Adherence: adherence will be assessed from pill counts when participant returns pills at each study visit after randomization. If only remote visits are permitted, then pill count will be completed when participant mails back drug bottles at the end of the study.
- Exit questionnaires will be administered at the last visit to determine global assessments of treatment, adequacy of informed consent procedures, satisfaction with study procedures and personnel, and opinions about the intervention.
- Blood specimens will be collected for fasting blood glucose and analysis of metabolic and oxidative markers related to asthma if a site permits this. Excess blood specimens will be used for future asthma research with the patient's consent. Fasting blood draw may take place within 7 days of rest of the procedures scheduled for visit 2 or visit 7.

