2.11. Modifications due to COVID-19 pandemic

Due to the COVID-19 public health emergency, TRIM, will permit remote follow up of enrolled participants as of April, 6, 2020. Participants enrolled after re-opening of the study should be seen at in-person visit for V2 (randomization visit) and V7 (24 weeks), other visits can be conducted in-part or fully remotely. It is possible that research activities will face restrictions in the future or that a participant will prefer to do the V4-V6 remotely, so we will provide participants with a scale and tape measure to collect data for remote visits. All questionnaires can be conducted remotely prior to in-person visits for all visits. Participants who are followed up remotely, will complete some questionnaires over the phone and mail back the rest of the questionnaires to the site. Methacholine challenge tests and spirometry should not be conducted. Women of child-bearing potential and participating in remote follow up will be mailed testing kit, and asked to send photo of result to coordinator

3. Data analysis

The appropriateness of the human, technological and systems components of the data acquisition and management procedures will be analyzed including practicality of data acquisition, estimation of likely participant characteristic and outcome distributions, suitability and functionality of paper and electronic forms, and resources required for participants contact and follow up, and to anticipate rates for missing data.

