3.2. Secondary outcomes

Secondary outcomes include ASUI, mAQLQ, and GSRS scores, lung function, weight loss and adverse events. Continuous outcomes, scores and lung function, will be analyzed similarly to the primary outcome. Event outcomes will be analyzed in two ways: negative binomial regression to estimate rates and Kaplan-Meier curves and Cox proportional hazard models for time-to-first event.

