Anticipated % patients experiencing an event compared to placebo if treated for 24 weeks with roflumilast 500 mcg per day (based on data above):

- diarrhea (9.7%)
- nausea (11.1%)
- insomnia (2.8%)
- headache (9.6%)
- dizziness (2.9%)

The psychiatric risks of roflumilast treatment are mitigated through the monitoring and management of symptoms as described below.

Weight loss is considered to be an advantageous outcome in the population being studied. *If a participant loses ≥ 10% of baseline weight during the course of the trial, this will be discussed with the study physician (preferably the study PI) as soon as possible.*

The GSRS will be used primarily to monitor GI side-effects, if a participant scores ≥ 6 on any item (indicative of severe or very severe discomfort), this will be discussed with the study doctor immediately, and the study PI as soon as possible.

The potential for drug interactions with roflumilast is mitigated through excluding participants on medications known to interact with roflumilast. We will exclude participants with uncontrolled anxiety and depression, and suicidal ideation, and screen for these at every visit, we will discontinue the patient from drug treatment if they develop these symptoms (threshold as defined in eligibility criteria). Plans for dealing with elevated symptoms of depression, anxiety and self-harm are outlined below.

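### Baseline weight has no stated visit or device, and no V2 reading on the take-home scale is specified, so remote weight changes probably carry the offset between two scales

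*Combined protocol and SAP*

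**What the plan says.** Section 2.9 makes weight part of a standard set of measurements: "Anthropometrics will include blood pressure, height and weight, and waist and hip circumference per NHANES III". The visit table marks this set at every visit from V1 to V7. The same section adds "Digital scales will be given to participants at visit 2 to take home to measure weight", and then "Participants will be asked to send a photo of the weight shown on the scale along with their feet to the coordinator".

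Section 2.11 gives the purpose of the scale: "we will provide participants with a scale and tape measure to collect data for remote visits". For participants who joined after the study re-opened, it asks for V2 and V7 in person and says of the rest that "other visits can be conducted in-part or fully remotely". It states no in-person requirement for those enrolled earlier, whose follow-up could be remote from 6 April 2020.

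Weight is then used in two ways:
- **As a tolerability check.** Section 4.1.1, repeated in 4.3, has the condition "If a participant loses ≥ 10% of baseline weight during the course of the trial". The consequence is a conversation with the study physician.
- **As an outcome.** Section 3.2 states "Secondary outcomes include ASUI, mAQLQ, and GSRS scores, lung function, weight loss and adverse events".

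Neither section says which visit or which scale supplies baseline weight. Nothing in the plan asks for a reading on the issued scale at V2, a paired reading on both scales, or a record of which device gave each weight.

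**The concern.** V2 is the in-person randomization visit, so a clinic weight is the natural baseline. A participant followed remotely after that has weights read from a different device. Each remote change from baseline then contains the true change plus whatever the two scales differ by.

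Two things are at stake. First, for a fully remote participant, V3 to V6 are the only scheduled weights on which the 10% check can be acted on before treatment ends. A home scale that reads high delays the check, and one that reads low brings it forward. Second, the offset adds variance to weight change at remote visits in a trial with only 19 participants per arm. Both costs are largely avoidable, because the scale and the participant are in the same room at V2.

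**Working it through.** The plan states no figure on this point, so there is none to reproduce.

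**Inputs from the documents.** The threshold is 10% of baseline weight (4.1.1, 4.3). There are 38 participants allocated 1:1 (1.3, 2.8), hence 19 per arm.

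**Assumed inputs (the documents give none of these).** Clinic baseline W = 100 kg, with 85 to 140 kg as a range. Offset b, home minus clinic, is constant within a participant, with 1.5 kg as the main case. Offset SD o = 1.0 to 1.5 kg. SD of true weight change s = 4 kg.

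**Step 1: the 10% check with a clinic baseline.** The home scale shows true weight + b. The check fires when true weight + b ≤ 0.9W, that is, at a true loss of 10% + b/W.
- b = +1.5 kg: true weight ≤ 90 − 1.5 = 88.5 kg, so it fires at 11.5%.
- b = −1.5 kg: true weight ≤ 90 + 1.5 = 91.5 kg, so it fires at 8.5%.

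**Step 2: the 10% check with a V2 baseline on the same home scale.** The baseline reading is W + b. The check fires at a true loss of 0.1(W + b), that is, 10% + 0.1b/W.
- b = +1.5 kg: 0.1 × 101.5 = 10.15 kg, so it fires at 10.15%.
- b = −1.5 kg: 0.1 × 98.5 = 9.85 kg, so it fires at 9.85%.

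A same-scale baseline therefore removes nine tenths of a constant offset from the percentage check, and all of it from the change in kg.

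**Step 3: sensitivity to body weight and offset.** True loss at which the check fires:

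| W (kg) | Offset (kg) | Clinic baseline | Same-scale baseline |
|---|---|---|---|
| 85 | ±1 | 8.82% to 11.18% | 9.88% to 10.12% |
| 85 | ±2 | 7.65% to 12.35% | 9.76% to 10.24% |
| 100 | ±1 | 9.0% to 11.0% | 9.9% to 10.1% |
| 100 | ±2 | 8.0% to 12.0% | 9.8% to 10.2% |
| 140 | ±2 | 8.57% to 11.43% | 9.86% to 10.14% |

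**Step 4: how often the check would be wrong.** With W = 100 kg and a normal offset with mean zero and SD o, the chance that the check fires at a true loss of L% is Φ((L − 10)/o). For o = 1 kg this is about 0 at a true 5% loss, 2.3% at 8% and 15.9% at 9%. At a true 11% loss it is 84.1%, so 15.9% are missed.

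**Step 5: precision of the weight outcome at a fully remote visit.** The standard error of the difference between arms is √(s² + o²) × √(2/19).
- No offset: 4 × 0.3244 = 1.298 kg.
- o = 1.0 kg: √17 × 0.3244 = 1.338 kg, a rise of 3.1%. The variance ratio is 17/16 = 1.06.
- o = 1.5 kg: √18.25 × 0.3244 = 1.386 kg, a rise of 6.8%. The variance ratio is 18.25/16 = 1.14.

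**Step 6: bias.** A mean offset common to the home scales shifts both arms equally and cancels from the treatment difference, provided remote visits are used similarly in the two arms. What remains is noise.

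**The case against.** The strongest reply is that this is an operational detail for a procedures manual in a 38-person pilot, and that the mixed-device comparison is inferred. Much of that stands.

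- **The clinic baseline is inferred.** A reader might take the plan to prescribe a home reading set against a clinic baseline. It does not: it names neither visit nor device, and it does not forbid reading the issued scale at V2. What is certain is that baseline weight is undefined and no paired reading is specified. Section 2.9 cites an anthropometry manual that is not available here, but the section itself says nothing about pairing the two scales.
- **The 24-week outcome.** A reader might infer that the main weight comparison is compromised. For participants who joined after re-opening, V2 and V7 are both planned in person, so that change is clinic against clinic. If weight is analysed like the other continuous outcomes, the 24-week term is the contrast of interest, and it compares like with like.
- **Bias between arms.** A reader might infer this too. Assignment is randomized and masked, and nothing in the documents suggests that remote visits differ by arm.
- **The safety consequence.** The check prompts a conversation and no automatic action, and section 4.1.1 regards weight loss as desirable in this population. Only participants within about 1 to 2 percentage points of the line are likely to be misclassified. The documents list weight loss as a label warning but do not call it dose-related, so no weight should be placed on that.
- **Limits of a paired reading.** It corrects the device component only. Clothing and floor surface at home still differ from the clinic.

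These points limit the scope but do not remove the gap. Followed as written, the V3 to V6 checks of a fully remote participant most naturally compare two scales.

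**Conclusion.** The point holds as a minor, cheap improvement; it is not an error or a contradiction in the plan. Baseline weight is undefined by visit and device, and the take-home scale is issued at V2 without a specified reading there. The consequence is confined to remote V3 to V6 and to any V7 that has to be remote, which is most plausible for participants enrolled before re-opening.

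Under the main assumed inputs, a 1.5 kg offset at 100 kg shifts the 10% check by 1.5 percentage points either way, and a same-scale baseline cuts that to 0.15. The loss of precision at remote visits is about 3% to 7% in standard error. These sizes depend wholly on assumed body weight, offset and SD of change, and on an offset that stays constant within a participant. That the offset is noise and not bias depends on similar remote use in the two arms. No view is taken on the 10% rule.

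**What to change.** In section 2.9:

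1. Define baseline weight as the V2 weight.
2. At V2, weigh the participant on the issued take-home scale directly after the clinic scale, and record both.
3. Record the device for every later weight.
4. For both the 10% check and the weight outcome, compare home readings with the V2 home-scale reading and clinic readings with the V2 clinic reading. Enter this device-matched change in the weight analysis, so that each participant contributes one change per visit.
5. For participants who received a scale after V2, take a paired reading at the next in-person visit, if there is one, and use it to correct their home readings. It cannot alter checks already made. Those with no further in-person visit remain uncorrected and should be flagged.

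The cost is about one minute and one form field at V2, plus a device entry with each later weight. The 10% rule and its clinical follow-up stay unchanged. Section 3 sets out to assess how practical data acquisition is, and the paired readings would also give the definitive trial an estimate of the home-to-clinic offset.
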